The present study will elucidate whether the presence of five common radiological bowel signs on CT, either alone or in combination, may distinguish between no bowel ischaemia (suspected AMI) vs. reversible (AMI treated without bowel resection) vs. irreversible ischaemic damage (AMI treated with bowel resection).

To accomplish this, CT scans from patients enrolled in the multicentre international study (The AMESI study, Clinical Trials: NCT05218863) will be collected and subjected to retrospective analysis by the investigating radiologists. After analysing predefined radiological signs separately for their association with the need for bowel resection, the feasibility of combining different CT findings will be explored with the goal of **establishing a practical CT-based radiological scoring system for separating patients with reversible and irreversible bowel ischaemic damage.**

As different subtypes (arterial, venous, and non-occlusive mesenteric ischemia) have different pathoanatomical courses, differences in radiological bowel signs may be expected. To overcome this variability, we will first elaborate the score based on all patients with a confirmed diagnosis of AMI. As a second stage, we will test the score by including only patients with arterial occlusive AMI. If these two created scores appear to be different, we will test them mutually and in subgroups of other subtypes of AMI. The ultimate goal is to have one radiological score identifying the magnitude of bowel damage that could be used for any form of AMI, with possible minimized adaptations needed subtypes.

Considering the low number of venous AMI and NOMI we will primarily not create separate scores for these subtypes. If the performance of created scores appears insufficient in our study, these subtypes need to be assessed in a separate study.

Objectives

The primary objective of the study is to **create a CT-based AMI score using radiological signs that would enable the differentiation between patients with salvageable and non-salvageable ischemic bowel damage.**

The specific objectives are as follows:

- To describe the prevalence of common radiological bowel signs (Table) in AMI patients with and without irreversible ischaemic damage of the bowel.
- To assess the prognostic capability of these radiological bowel signs, both individually and in combination, for predicting irreversible ischaemic damage of the bowel.

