- To describe the prevalence of common radiological bowel signs in patients with confirmed AMI vs. suspected but eventually non-confirmed diagnosis of AMI
- To describe the prevalence of common radiological bowel signs in patients with different subtypes of AMI (arterial occlusive, venous, NOMI, other/unclear).

Study questions

- 1) What is the frequency rate of common radiological bowel signs (Table 1) among AMI patients with and without salvageable bowel?
- 2) Is it possible to distinguish the AMI patients with and without salvageable bowel with the use of a CT-based AMI score composed of common radiological signs?
- 3) Is it possible to differentiate the patients with and without AMI with the use of CT-based AMI score composed from common radiological signs?

Hypothesis

It is possible to differentiate between AMI patients with salvageable and non-salvageable ischemic bowel damage using the score based on CT radiological bowel signs.

Study outcomes

Primary study outcomes: Frequency rate of common radiological signs in AMI patients with and without salvageable bowel. Radiological score value in AMI patients according to the stage of bowel ischaemic damage.

Secondary study outcomes:

Frequency rate of common radiological signs/findings among patients with confirmed and suspected but eventually not confirmed AMI.

Performance of the radiological score in patients with different types of AMI.

Methods

This is a substudy of the AMESI study - "Incidence, Diagnosis, Management, and Outcome of Acute Mesenteric Ischaemia: A Prospective, Multicentre Observational Study." As of the end of August 2023, a total of 705 patients from 32 study sites worldwide have been enrolled, with 418 of them having confirmed cases of AMI. For patients with confirmed AMI, comprehensive data collection concerning diagnostics, management, and long-term outcomes has been completed (refer to Appendix 1).

Patients:

From the final AMESI cohort, we will select 6-7 sites limited to Europe due to logistical reasons related to the installation of software for the transmission of full CT investigations in impersonalized form. We expect to obtain images of at least 100 patients with confirmed AMI. Only study sites with more than 20 patients in total enrolled in the study will be asked to contribute radiological data. The CT scans will be gathered through AMESI's dedicated international online platform, and a retrospective visual and

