Inclusion Criteria: CT scan of the entire abdominal cavity / full body using intravenous contrast media.

Exclusion criteria: Scans without the use of an intravenous contrast media or those covering only a partial area of the abdomen will be excluded.

Two radiologists, who will be blinded to the original radiology report, clinical diagnosis and outcome of the patient, will review the CT scans. The CT images will be screened for radiological signs indicative of mesenteric ischaemia (Table 1). The presence of these signs will be recorded as indicated in the Table. In order to develop a radiological score, the bowel signs are used.

Statistics

Obtaining radiological data:

Interobserver agreement for CT findings will be determined with the κ statistic and classified as follows: $\kappa = 0\text{--}0.2$, slight agreement; $\kappa = 0.21\text{--}0.4$, fair agreement; $\kappa = 0.41\text{--}0.6$, moderate agreement; $\kappa = 0.61\text{--}0.8$, substantial agreement; and $\kappa = 0.81\text{--}1$, almost perfect agreement.

Disagreements between the two reviewers will be resolved by consensus. Consensual data will then be used for final statistics.

Descriptive statistics:

We will compare epidemiological data and CT signs between patients with and without salvageable bowel damage. Pearson Chi-square or Fisher tests will be used for the comparison of categorical variables, and the Student t-test or Wilcoxon rank-sum test for the comparison of continuous variables as appropriate. A frequency table for the occurrence of radiological symptoms in study groups will be constructed.

Workout of radiological CT-score

In order to develop a radiological score, the bowel signs are used (Table 1, 3-7). We will compare CT signs

- 1) between the patients with salvageable and non-salvageable bowel damage;
- 2) between the patients with confirmed and suspected but eventually not confirmed AMI. The conceptual approach is presented in Figure 1.

[figure not shown]

Figure 1. Conceptual approach for radiological score.

Pearson Chi-square or Fisher tests will be used for the comparison of categorical variables, and Student t-test or Wilcoxon rank-sum test for the comparison of continuous variables as appropriate.

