All CT findings with a univariate p -value ≤ 0.1 were entered into a multivariate logistic regression model to gauge their independent association with non-salvageable bowel damage (comparison 1) or confirmed diagnosis of AMI (comparison 2). The radiological score will be constructed based on univariate logistic regression models, where the dependent variable will be non-salvageable bowel and the independent variable will be radiological sign. The number of models will be equal to the number of radiological signs. The coefficient from the model will be uprounded and used as a weight for the radiological sign. In case the weights from the univariate models are clinically not relevant, expert opinions will be used instead. All the radiological signs will then be multiplied with the assigned weights and then summed. Finally, one by one the radiological signs will be left out of the score to test, whether a simpler version of the score would also give as good results as the more complicated version. The goodness of the score will be evaluated using AUC. A similar score will be constructed for suspected vs confirmed AMI.

However, if this will not result in a useful score, we will use a more complicated approach based on interactions between the radiological signs and interpretations of the results from the simpler approach.

In the first approach, **two scores** will be constructed.

- 1) using data of all patients with confirmed AMI
- 2) using data of only patients with confirmed arterial occlusive AMI

The performance of these two score will be tested in the following cohorts:

- a) all patients with confirmed AMI
- b) only occlusive arterial AMI included
- c) only non-occlusive AMI included
- d) Patients with venous occlusive AMI excluded
- e) Patients subjected to palliative care excluded

Table 1. Common radiological signs used to detect bowel ischaemia in CT imaging

	Radiological sign	Description
Vascular signs:		
1.	Occlusion of superior/inferior mesenteric artery/or its respective branches	No contrast enhancement on MDCT scan in the arterial phase or in the venous phase/lack of contrast enhancement within the vessel lumen / Acute arterial thrombi and emboli may appear as obvious low-attenuation filling defects in the SMA, its branches, or other major mesenteric arteries.

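### Palliated patients are removed only when the scores are tested, so a resection-based label can carry unresected necrotic bowel into the weights and sign frequencies as salvageable

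*Protocol*

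**What the plan says.** **Label.** The Background separates "reversible (AMI treated without bowel resection) vs. irreversible ischaemic damage (AMI treated with bowel resection". Under Allocation of patients into study groups, the salvageable group is introduced as confirmed AMI in which no resection was done. Items 3 (exploration) and 4 (conservative treatment) of the list in that table are worded differently: they turn on resection not having been needed. The Background also speaks once of the need for resection.

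**Who is analysed.** The exclusion criteria under Radiological Methods concern the scan only: "Scans without the use of an intravenous contrast media or those covering only a partial area of the abdomen will be excluded".

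**Primary outcome.** The first primary outcome is "Frequency rate of common radiological signs in AMI patients with and without salvageable bowel". Descriptive statistics repeats it: "We will compare epidemiological data and CT signs between patients with and without salvageable bowel damage". Neither place restricts on palliative care.

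**Weights.** Under Workout of radiological CT-score, the dependent variable is non-salvageable bowel. Each sign's univariate logistic coefficient is rounded up to give its weight. Score 1 is built "using data of all patients with confirmed AMI", and score 2 "using data of only patients with confirmed arterial occlusive AMI".

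**Palliative care.** It is mentioned once, as cohort (e): "Patients subjected to palliative care excluded". The list it belongs to is introduced by "The performance of these two score will be tested in the following cohorts", so it governs testing of finished scores and not their derivation.

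**The concern.** The primary objective concerns the state of the bowel: salvageable or not. Whether a resection was done is a proxy for that state. The proxy can fail in palliated patients, because necrotic bowel may be left in place, or the bowel may never have been inspected. Cohort (e) shows that the authors expect such patients in the confirmed-AMI set and want to see results without them, but the restriction comes after the weights and the frequency table have been produced.

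If the resection-based label is applied, necrotic bowel in the salvageable group brings its signs with it. Three reported results would move: sign frequencies in the salvageable group go up, univariate weights go towards zero, and the AUC in every cohort that keeps these patients goes down. Cohort (e) would reveal most of the AUC distortion. It cannot correct the weights or the frequencies.

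**Working it through.** The Protocol gives no figure for this point to reproduce, so the check is an illustration.

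**Inputs**
- Single-sign sensitivity 30% to 40% and specificity up to 98% (Background). I use 35% sensitivity with 98% specificity as the stated ceiling; 95% and 90% specificity are assumptions.
- 50 patients per group, the lower end of the targets in the allocation table.
- m, the share of the labelled-salvageable group whose bowel is necrotic. The Protocol gives no such figure; 5, 10 and 20% are assumed.

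**One sign**

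Frequency in the labelled-salvageable group: p0 = (1 − m)(1 − spec) + m × sens. Coefficient: b = logit(sens) − logit(p0). Weight: b rounded up, as the Protocol prescribes.

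Example at 98% and m = 10%: p0 = 0.90 × 0.02 + 0.10 × 0.35 = 0.053, and b = logit(0.35) − logit(0.053) = 2.26, giving weight 3.

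| m | spec 98%: p0, b, weight | spec 95%: weight | spec 90%: p0, b, weight |
|---|---|---|---|
| 0 | 2.0%, 3.27, 4 | 3 | 10.0%, 1.58, 2 |
| 5% | 3.7%, 2.65, 3 | 3 | 11.3%, 1.45, 2 |
| 10% | 5.3%, 2.26, 3 | 2 | 12.5%, 1.33, 2 |
| 20% | 8.6%, 1.74, 2 | 2 | 15.0%, 1.12, 2 |

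**Against sampling error**

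SE(b) = √[1/(50 × 0.35) + 1/(50 × 0.65) + 1/(n0(1 − spec)) + 1/(n0 × spec)]. With n0 = 50 this is 1.05 at 98% and 0.56 at 90%. The shift at 98% and m = 10% is 3.27 − 2.26 = 1.01, about one standard error. This is a systematic bias that a single study of this size could not detect.

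**Five signs together**

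Assume independent signs with sensitivities 35/40/35/30/40% and specificities 90/90/98/98/95%. Weights are 2,2,4,4,3 at m = 0; 2,2,3,3,3 at 5%; 2,2,3,3,2 at 10%; and 2,2,2,2,2 at 20%. The exact AUC over the 32 sign patterns is:

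| m | AUC against the label (all AMI) | AUC against true bowel state |
|---|---|---|
| 0 | 0.897 | 0.897 |
| 5% | 0.876 | 0.896 |
| 10% | 0.854 | 0.893 |
| 20% | 0.807 | 0.884 |

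The loss of true discrimination is at most 0.897 − 0.884 = 0.013.

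**With sampling error**

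In 2,000 simulated studies (50 per group, 0/2/5/10 of the labelled-salvageable patients having necrotic bowel, 0.5 added to each cell), the mean weight of the 98% sign was 3.62/3.17/2.75/2.24 and of the 90% sign 2.10/1.96/1.83/1.60. The reported all-AMI AUC was 0.901/0.885/0.861/0.824. With the mislabelled patients removed from testing only, as in cohort (e), it was 0.901/0.899/0.897/0.896. So cohort (e) recovers the AUC while the weights stay shrunken.

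**The case against.** The strongest objection is that the decisive text is lost. In the allocation table two cells each open a list, but only one four-item list survives. All four items describe unresected patients, yet they stand in the non-salvageable cell, so this looks like damage from text extraction. A non-salvageable definition with several routes suggests that resection need not be the only one, and documented necrosis left in place may be among them. A reader might infer that the plan has no rule for such patients, or that it certainly labels them salvageable. The documents support neither, since what is unreadable here is not missing from the plan.

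Second, items 3 and 4 turn on need, and necrotic bowel found at exploration does not naturally meet a no-need condition. That is fair, but the Background and the lead-in for the salvageable group turn on what was done. No readable text says how need is judged when care was palliative or the bowel was never seen.

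Third, keeping palliated patients in the derivation is not itself an error. If those with necrosis are labelled non-salvageable, they belong there. This stands, and the remedy should not remove palliated patients wholesale.

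Fourth, the effect is modest. The drop from 4 to 2 uses the ceiling specificity. With 50 salvageable patients and no mislabelling, a 98%-specific sign already has a 36% chance (0.98^50) of never appearing in that group, so its plain logistic coefficient would not be finite. The Protocol also allows expert weights, which these figures ignore. All of this limits the severity.

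Detailed handling of indeterminate patients could also be left to an SAP. But the Protocol itself fixes the label, the derivation sets and the test cohorts, and the point concerns what it fixes.

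**Conclusion.** The point holds conditionally and is minor to moderate. The readable Protocol words its label in ways that need not agree, derives both scores from confirmed AMI including palliated patients, and removes them only when finished scores are tested. If the Background label is applied as written, unresected necrotic bowel is fitted and counted as salvageable. Whatever the unreadable list says about documented necrosis, a palliated patient whose bowel was never assessed has no sound reference label for the derivation.

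The size rests on an assumed mislabelled share of 5 to 20%, on mislabelling being the only error and, for the AUCs, on independent signs. Under those assumptions the harm lies in the published weights, the salvageable-group frequencies and the all-AMI AUC. A reader might infer that the score itself would discriminate much worse; the figures do not support that. Nothing is claimed about early deaths not recorded as palliative, or about the score for suspected versus confirmed AMI.

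**What to change.** 1. Reconcile the three wordings (treated without resection, resection not done, resection not needed) into one label based on bowel state. Unresected patients with necrosis documented in the data already retrieved count as non-salvageable. Data collection lists management, histology and outcome data; whether these record bowel state in every unresected patient cannot be seen here.
2. Derive both sets of weights and the primary sign-frequency table without unresected palliated patients whose bowel state was not assessed. Palliated patients with a known bowel state stay in.
3. As sensitivity analyses, report the current resection-based label, and assign the indeterminate patients all to salvageable and then all to non-salvageable.
4. Keep cohorts (a) and (e) for testing.

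**Cost.** Protocol wording and recoding, plus a slightly smaller derivation set. If 5, 10 or 15 of 50 salvageable patients are left out, the standard error of a log odds ratio goes from 0.56 to 0.58, 0.60 or 0.64 at 90% specificity, and from 1.05 to 1.11, 1.17 or 1.24 at 98%.

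The AUC may also become optimistic, because unclear cases are left out and palliation is decided after the CT. The two-way analyses would show this. With 10 of 50 indeterminate and half of them necrotic, the 98% sign's coefficient is 2.26 (all salvageable, p0 = (45 × 0.02 + 5 × 0.35)/50 = 0.053), 3.27 (left out) or 3.15 (all non-salvageable, p1 = (55 × 0.35 + 5 × 0.02)/60 = 0.3225). For the 90% sign it is 1.33, 1.58 or 1.49.

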CT with contrast media enhancement has become the most accurate technique for diagnosing AMI, with a reported specificity between 90 and 100% [3,4], and is considered the first-line imaging modality when AMI is suspected. In addition to recognition of AMI, CT imaging has the potential to differentiate between reversible and irreversible ischaemic intestinal damage [5, 6]. **This is a pivotal moment in choosing the treatment strategy** – in the absence of irreversible damage; reperfusion therapy can restore intestinal viability and thus avoid bowel resection.

Various radiological signs are routinely used to detect bowel ischaemia in CT imaging. The list includes vascular – occlusion of mesenteric arteries or veins – and bowel signs – bowel dilatation, decreased or absent bowel wall enhancement, pneumatosis intestinalis, gas in the mesenteric or portal veins, and bowel wall thinning (Table 1). The capability of these signs to describe the stage of ischaemia has been addressed in some studies. A recent meta-analysis demonstrated that bowel wall thinning, decreased or absent bowel wall enhancement, bowel dilation, pneumatosis intestinalis, porto-mesenteric venous gas, and mesenteric artery occlusion are independent risk factors predicting transmural necrosis (5), whereas decreased or absent bowel wall enhancement and bowel dilation were predictive for

transmural necrosis also in venous occlusive AMI. The same meta-analysis showed that bowel wall thickening and increased bowel wall enhancement were not predictive of transmural necrosis (5). Importantly, while the specificity of these radiological findings, when considered individually, is considerably high—up to 98%—the sensitivity remains very low, ranging from 30% to 40% (5).

Based on this, we hypothesize that **combining multiple signs may enhance the diagnostic performance of CT scanning in distinguishing various stages of ischemic bowel damage.**

From a practical perspective, it is important to predict who **requires bowel resection** and who has **potentially salvageable bowel**. Bowel resection is a disabling surgery that significantly affects a patient's quality of life. Whenever possible, it should be avoided. If the bowel is salvageable, an endovascular procedure can restore mesenteric blood supply – this allows avoiding laparotomy and is considerably less traumatic for the patient.

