The AMESI database of pseudonymized CT-s can be accessed via an online platform with the personal identification of selected and authorized study group members. For participants in the AMESI study, the consent to use the clinical and imaging data has been obtained or waived at enrolment, based on local ethics rules. A centralized collection of radiological images was planned in the study protocol of the AMESI study. Installation of software for pseudonymizing CT images will require additional institutional approval from each site.

Data collection:

Patients' clinical and demographic characteristics, including baseline data, AMI event data, management data, histology data, and hospital outcome data will be retrieved from the RedCap database of the AMESI study (Appendix 2), or from the Tartu University Hospital patient data management system.

Data Retention:

The data collected during the study will be stored securely on Tartu University servers till 31.12.2039 and will be securely removed after this date. Only authorised study team members will have access to the data.

Allocation of patients into study groups:

To test the hypothesis, the study patients will be divided into the following study groups:

	Control Cases	Patients with confirmed AMI. Target: 100 - 200	
		AMI patients with salvageable bowel	AMI patients with non-salvageable bowel
No of pt	Target: 50-100	Target: 50-100	Target: 50-100

Definition of the patient group	Patients included in the AMESI study as suspected AMI	Patients included in the AMESI study with confirmed AMI, who did not undergo bowel resection Patients with one of the following:	Patients included in the AMESI study with confirmed AMI who (one of the following): 
 1) treated endovascularly and did not undergo bowel resection secondarily 2) received surgical revascularization without bowel resection (initial or secondary) 3) received explorative laparoscopy or laparotomy without the need for bowel resection (initially or secondarily) 4) received conservative treatment without the need for secondary bowel resection
---------------------------------	---	--	---

Radiological Methods:

CT scans with intravenous contrast media relevant to the hospitalization of selected patients from the AMESI study cohort will be pseudonymized and uploaded to the online AMESI database. The selection of CT scans will be based on the initial diagnostic hypothesis of acute abdomen or suspicion of AMI.

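### The score is fitted to whether bowel was resected, although its stated target is bowel viability, and no use is stated for the histology that is retrieved

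*Protocol*

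**What the plan says.** The Background of the protocol sets out the groups by treatment received: "reversible (AMI treated without bowel resection") against "irreversible ischaemic damage (AMI treated with bowel resection"). The table under Allocation of patients into study groups follows the same line for the salvageable group: "Patients included in the AMESI study with confirmed AMI, who did not undergo bowel resection". Under Workout of radiological CT-score, non-salvageable bowel is the dependent variable. One univariate logistic model is fitted per sign, its coefficient is rounded up to give the weight, and the score is judged by AUC.

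The Background states that "CT imaging has the potential to differentiate between reversible and irreversible ischaemic intestinal damage", treats this distinction as decisive for the choice of treatment, and describes the signs as part of routine reading. Under Radiological Methods, the scans to be scored come from the diagnostic work-up, and the study radiologists are "blinded to the original radiology report, clinical diagnosis and outcome of the patient".

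Under Data collection, "management data, histology data, and hospital outcome data will be retrieved from the RedCap database of the AMESI study". That is the only mention of histology as study data. No readable group definition, outcome, model or test cohort uses it; the five test cohorts differ only by AMI subtype and palliation.

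**The concern.** Viability is a state of the tissue, and resection is something done to the patient. The two agree only as far as every resected bowel was irreversibly damaged and every unresected bowel was not. If the decision to resect was influenced by the same CT signs that enter the score, part of each fitted weight reflects how clinicians responded to the sign rather than what the sign says about the bowel. Blinding the study readers protects the reading of the signs; it does nothing for the label.

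Verification is also uneven. Unresected patients who had laparoscopy or laparotomy were inspected. For those treated endovascularly or conservatively, for example "received conservative treatment without the need for secondary bowel resection", the label rests on the later course alone.

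At stake is what the study may conclude. A score fitted and tested against resection supports a statement about who was resected. A statement about irreversible damage needs a further step, and the histology could supply part of it.

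**Working it through.** The protocol gives no figure on this point to reproduce. The check has two parts: how the label could depend on the signs, and what such dependence would do to a weight.

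**Route of dependence.** Two statements in the Background (signs in routine use; CT distinction decisive for treatment) and one under Radiological Methods (work-up scans are scored) make it likely that treating teams knew the CT findings. This is an inference. A sign that merely prompts an operation does not distort the label, because patients operated on without resection count as salvageable. Distortion needs viable bowel to be resected, or necrotic bowel to be left. Where such errors depend on the sign, the result can be pushed in either direction.

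**Illustration 1 (all inputs assumed).** There are 50 necrotic bowels, all resected, and 50 viable bowels. The sign is present in 40% of the necrotic (20 with, 30 without) and 20% of the viable (10 with, 40 without).

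- True OR = 20×40/(30×10) = 2.67; coefficient ln 2.67 = 0.98, rounded up to 1.
- Viable bowel resected in 30% with the sign (3 of 10) and 5% without (2 of 40): OR = 23×38/(32×7) = 3.90; coefficient 1.36, rounded up to 2.
- Resected in 20% and 5%: OR = 22×38/(32×8) = 3.27; coefficient 1.18, rounded up to 2.
- Resected in 15% regardless of the sign: OR = 21.5×34/(36×8.5) = 2.39; coefficient 0.87, rounded up to 1. The bias is now downward.
- Sign unrelated to necrosis (20% in both groups): OR = 13×38/(42×7) = 1.68 at 30%/5% and 12×38/(42×8) = 1.36 at 20%/5%; coefficients 0.52 and 0.31, both rounded up to 1.

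The step from weight 1 to weight 2 is fragile. With the sign in 42% of the necrotic (21 with, 29 without), the true OR is 21×40/(29×10) = 2.90 (coefficient 1.06) and the 30%/5% OR is 24×38/(31×7) = 4.20 (coefficient 1.44). Both round up to 2.

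**Illustration 2.** Sensitivity of 30–40% and specificity of up to 98% are the Background's figures for single signs. Specificity of 90%, necrosis in 50% and all resection probabilities are assumed. The coefficient is the log odds ratio of the sign against resection; the single-sign AUC is (apparent sensitivity + apparent specificity)/2.

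| Resection probability (sign present / absent) | Sens/spec | ln OR, true → apparent | AUC, true → apparent |
|---|---|---|---|
| Necrotic 0.98/0.80, viable 0.40/0.05 | 35%/90% | 1.58 → 2.30 | 0.625 → 0.670 |
| Same | 35%/98% | 3.27 → 3.54 | 0.665 → 0.682 |
| Necrotic 0.90/0.90, viable 0.10/0.10 | 35%/90% | 1.58 → 1.22 | 0.625 → 0.600 |
| Necrotic 0.70/0.90, viable 0.05/0.05 | 35%/90% | 1.58 → 0.60 | 0.625 → 0.553 |

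At 98% specificity the rounded weight stays at 4. Across sensitivities of 30–40%, the AUC rises by about 0.02 to 0.05 under the first set of probabilities. A sign with no information on necrosis (30% in both groups) would show ln OR 1.10 and AUC 0.61 under that set.

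**What histology can and cannot repair.** In illustration 1 at 30%/5%, removing the 5 viable resected cases from the non-salvageable group, with the unresected group unchanged, gives 20×38/(30×7) = 3.62. This moves from 3.90 towards 2.67 without reaching it, because the unresected group has lost its sign-positive viable cases.

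**The case against.** Several points on the other side stand.

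- **The proxy is declared.** The Background names the need for resection as the practical question, and the readable criteria also require no secondary resection, which is a form of follow-up. This makes the label useful. It does not turn receipt of resection into irreversible damage.
- **Resection is often decided on findings at operation.** A reader might infer that signs gain weight simply because they trigger surgery. The documents do not support that, since exploration without resection counts as salvageable. Nothing in them shows how often viable bowel is resected, or whether that depends on a sign.
- **A reader might infer that histology plays no part in the definition.** That cannot be said. The allocation table has lost its layout in the available text: the non-salvageable cell shows no-resection criteria, so its own list cannot be seen. Figure 1 and the appendices are also not shown. What can be said is that no use is stated in the readable text. The Background definition is intact.
- **The figures rest on assumed probabilities,** the weight change is sensitive to small shifts, and expert weights may replace fitted ones.
- **Details may be left to an SAP.** A supplementary cohort could be. But the protocol itself fixes the label and the objective, and these two differ.

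**Conclusion.** The concern holds in a limited form. The protocol fits weights and AUC to resection and aims at viability. Some dependence of the label on the predictors is plausible but not demonstrated, and reader blinding does not address it. Its direction and size are unknown: in the illustrations, an odds ratio of 2.67 appears as 2.39 to 3.90, and a coefficient of 1.58 as 0.60 to 2.30, according to resection probabilities that the documents do not give.

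A reader might go on to conclude that the score will overweight certain signs, or that its AUC will be inflated. The documents support neither. The defect does not invalidate the resection-defined analysis; it limits what that analysis can be said to show.

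**What to change.** Keep the resection-defined analysis as primary and add one sensitivity analysis to the list of test cohorts under Workout of radiological CT-score:

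- Non-salvageable means resected with transmural necrosis in the AMESI histology record.
- Resected patients whose histology shows no transmural necrosis are not counted as irreversible. Those without usable histology are reported separately.
- The unresected group stays as defined.
- Report the number of resected patients without confirmed transmural necrosis. Show weights and AUC with confidence intervals beside the primary result.
- Describe the primary score as predicting bowel resection, and the histology analysis as showing how far this extends to irreversible damage. Do not tie the wording to whether the two results differ: without a tolerance, they almost always will.

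State the limits: histology exists only where tissue was taken, so it cannot confirm viability in unresected patients, and the correction is partial. A comparison restricted to operated patients may be shown as exploratory, with its selection stated, since the signs may influence who is operated on. In unresected operated patients the criteria record that no resection was done, not that the bowel was seen to be viable.

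The cost is one further analysis with no new image reading. There will be fewer non-salvageable cases than the targeted 50–100 and wider intervals. How many fewer depends on the completeness of the histology and on whether it grades transmural necrosis, neither of which the protocol states.
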